b Participants who discontinue the study treatment prematurely (prior to completing the 52-week treatment period) will perform the EOT assessments at the time of discontinuation to assure a complete clinical assessment in close temporal proximity to the premature termination of study treatment. In addition, to allow assessment of participant outcomes over the stipulated study period, participants will be asked and encouraged to complete all remaining study visits and participate in all assessments according to the visit schedule.

c If a participant discontinues treatment period prematurely before Week 40 but completes follow-up to Week 52, he/she will be considered to have completed the study.

d Consent to be obtained for optional procedures (whole blood DNA and whole blood RNA sampling and serum/plasma sampling for archival; HIV test if specific consent locally required, spirometry for children).

e Past medical history including allergic comorbidities (asthma, aspirin sensitivity, allergic rhinitis etc). Surgeries will be assessed including type and dates of sino-nasal surgeries, in the past. Systemic corticosteroids (SCS) use (number of courses, doses, way of administration and duration) in the past 2 years before V1 and/or contraindication/intolerance to SCS, as well as long-term antibiotics use (>2 weeks) in the previous year will be entered in the eCRF. Fungal stain assessment (positive/negative/not done).

f Details on actual or planned date for surgery type and outcome (whenever possible) of surgery will be recorded in a specific eCRF page. If surgery is performed during the study treatment period or follow-up an AE or SAE page will be completed. Participants will be discontinued from study treatment and assessed as soon as possible using the procedures normally planned for the EOT Visit. If surgery is scheduled after the planned end of study, a follow-up contact(s) may be required to document the surgery date and outcome.

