8.1.1.2 Three-dimensional volumetric measurement of the sinuses

This method is used to calculate: (37)

- The volume of the air (mL)
- The volume of mucosa (mL)
- % occupied by disease
- Thickness of lateral wall

For the analysis, central reading at baseline will be used for comparison with EOT reading. The sites will remove participant-identifying information from the imaging data header prior to sending the imaging data to the central reader. The % change in opacification from baseline to EOT will be calculated.

8.1.2 Proportion of participants who receive SCS and/or undergo/plan to undergo surgery for AFRS during the planned study treatment period

Systemic corticosteroids use

Use of systemic steroids for rescue treatment of AFRS or for another reason will be captured by the Investigator (or designee) on the appropriate page(s) of the eCRF page and the date and dosing information (daily dose, duration, INN). The reason for SCS use will be also captured.

Surgery (actual or planned) for AFRS

For participants who undergo or plan to have surgery for AFRS, the reason (worsening signs and/or symptoms during the study), the expected and real surgery date, the type and outcome of surgery will be recorded in a specific eCRF page. If surgery:

- Is performed during the study treatment period, participant and Investigator may decide to continue IMP up to the time of surgery or EOT whichever date comes first. At the time of surgery, participants will be permanently discontinued from study treatment and assessed as soon as possible using the procedures normally planned for the EOT Visit and will be instructed to return to the study site as described in [Section 1.3](#).
- Is performed during the follow-up the participants will be assessed according to the procedures normally planned for the EOS Visit and will be instructed to return to the study site as described in [Section 1.3](#).
- Date is scheduled after the planned end of study; a follow-up contact(s) will be scheduled around the time of planned surgery to document the surgery date and outcome.

8.1.3 Nasal symptom diary, including nasal congestion/obstruction, loss of smell, and anterior and posterior rhinorrhea

The Nasal Symptom Diary is designed to assess the severity of CRS nasal symptoms on daily basis. These symptoms include nasal congestion/obstruction, loss of smell, anterior rhinorrhea and posterior rhinorrhea (38). Each of the individual items of the diary are scored from

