10.3.1 Definition of AE

AE definition

- An AE is any untoward medical occurrence in a patient or clinical study participant, temporally associated with the use of study intervention, whether or not considered related to the study intervention.
- NOTE: An AE can therefore be any unfavorable and unintended sign (including an abnormal laboratory finding), symptom, or disease (new or exacerbated) temporally associated with the use of study intervention.

Events meeting the AE definition

- Any abnormal laboratory test results (hematology, clinical chemistry, or urinalysis) or other safety assessments (eg, ECG, radiological scans, vital signs measurements), including those that worsen from baseline, considered clinically significant in the medical and scientific judgment of the Investigator (ie, not related to progression of underlying disease).
- Exacerbation of a chronic or intermittent pre-existing condition including either an increase in frequency and/or intensity of the condition.
- New conditions detected or diagnosed after study intervention administration even though it may have been present before the start of the study.
- Signs, symptoms, or the clinical sequelae of a suspected drug-drug interaction.
- Signs, symptoms, or the clinical sequelae of a suspected overdose of either study intervention or a concomitant medication.
- “Lack of efficacy” or “failure of expected pharmacological action” per se will not be reported as an AE or SAE. Such instances will be captured in the efficacy assessments. However, the signs, symptoms, and/or clinical sequelae resulting from lack of efficacy will be reported as AE or SAE if they fulfill the definition of an AE or SAE.
- The signs, symptoms, and/or clinical sequelae resulting from lack of efficacy will be reported as AE or SAE if they fulfill the definition of an AE or SAE. Also, “lack of efficacy” or “failure of expected pharmacological action” also constitutes an AE or SAE.

Events NOT meeting the AE definition

- Any clinically significant abnormal laboratory findings or other abnormal safety assessments which are associated with the underlying disease, unless judged by the Investigator to be more severe than expected for the participant’s condition.

- The disease/disorder being studied or expected progression, signs, or symptoms of the disease/disorder being studied, unless more severe than expected for the participant's condition.

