- Medical or surgical procedure (eg, endoscopy, appendectomy): the condition that leads to the procedure is the AE.
- Situations in which an untoward medical occurrence did not occur (social and/or convenience admission to a hospital).
- Anticipated day-to-day fluctuations of pre-existing disease(s) or condition(s) present or detected at the start of the study that do not worsen.

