10.3.2 Definition of SAE

If an event is not an AE per definition above, then it cannot be an SAE even if serious conditions are met (eg, hospitalization for signs/symptoms of the disease under study, death due to progression of disease); however, if local health authority requirements supersede this it will be reported per local health authority requirements.

A SAE is defined as any untoward medical occurrence that, at any dose:

- a) **Results in death**
- b) **Is life-threatening**

The term “life-threatening” in the definition of “serious” refers to an event in which the participant was at risk of death at the time of the event. It does not refer to an event, which hypothetically might have caused death, if it were more severe.

- c) **Requires inpatient hospitalization or prolongation of existing hospitalization**

In general, hospitalization signifies that the participant has been detained (usually involving at least an overnight stay) at the hospital or emergency ward for observation and/or treatment that would not have been appropriate in the physician's office or outpatient setting. Complications that occur during hospitalization are AEs. If a complication prolongs hospitalization or fulfills any other serious criteria, the event is serious. When in doubt as to whether “hospitalization” occurred or was necessary, the AE should be considered serious.

Hospitalization for elective treatment of a pre-existing condition that did not worsen from baseline is not considered an AE.

- d) **Results in persistent disability/incapacity**

- The term disability means a substantial disruption of a person's ability to conduct normal life functions.
- This definition is not intended to include experiences of relatively minor medical significance such as uncomplicated headache, nausea, vomiting, diarrhea, influenza, and accidental trauma (eg, sprained ankle) which may interfere with or prevent everyday life functions but do not constitute a substantial disruption.
- Is a congenital anomaly/birth defect

e) Other situations:

- Medical or scientific judgment should be exercised in deciding whether SAE reporting is appropriate in other situations such as important medical events that may not be immediately life-threatening or result in death or hospitalization but may jeopardize the participant or may require medical or surgical intervention to prevent one of the other outcomes listed in the above definition. These events should usually be considered serious.

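### The protocol gives conflicting rules on whether, and under what term, surgery for AFRS leads to an AE or SAE record, so surgery-linked entries may reach the safety tables unevenly

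*Protocol*

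**What the plan says.** **Protocol 1.3, footnote f.** Surgery details go on a specific eCRF page, and in addition: "If surgery is performed during the study treatment period or follow-up an AE or SAE page will be completed". No criterion is given for choosing between an AE and an SAE page.

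**Protocol 8.1.2.** For surgery done or planned for AFRS, the reason (worsening during the study), the dates, and "the type and outcome of surgery will be recorded in a specific eCRF page". No AE or SAE page is mentioned.

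**Protocol 10.3.1** has five relevant statements:
- Among events that are not AEs: "Medical or surgical procedure (eg, endoscopy, appendectomy): the condition that leads to the procedure is the AE".
- Also among events that are not AEs: "The disease/disorder being studied or expected progression, signs, or symptoms of the disease/disorder being studied, unless more severe than expected" for that participant.
- Among events that are AEs: "Exacerbation of a chronic or intermittent pre-existing condition including either an increase in frequency and/or intensity of the condition".
- Lack of efficacy "per se will not be reported as an AE or SAE", although its signs, symptoms and sequelae are reported if they meet the definition.
- The next bullet ends by saying that lack of efficacy "also constitutes an AE or SAE".

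**Protocol 10.3.2.** "If an event is not an AE per definition above, then it cannot be an SAE even if serious conditions are met". Hospitalization for the disease under study is one of its examples. Local health authority requirements take precedence.

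**SAP 3.6 and 3.6.2.** Safety analysis is descriptive, without testing. TEAEs are the primary AE analysis, with tables of serious TEAEs and of TEAEs leading to permanent discontinuation. No rule identifies entries made because of AFRS worsening or surgery.

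**The concern.** Surgery for AFRS is an efficacy outcome. It is part of the rescue secondary endpoint, and the primary LMK analysis handles it as an intercurrent event by the composite strategy. Protocol 3.1 reports that dupilumab markedly lowered the proportion needing surgery in the CRSwNP program, so the plan itself gives reason to expect more surgery on placebo.

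If each surgery leads to an AE or SAE page at some sites and not at others, two things follow. Part of the between-arm safety comparison restates the efficacy result, and how large that part is depends on which rule a site followed. An SAE entry also starts 24-hour reporting to the sponsor (Protocol 8.3.1), so the difference is operational as well as tabular.

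**Working it through.** The plan states no figure to reproduce. The check is a comparison of texts, followed by simple division.

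**Step 1. Apply each rule to one case:** a participant whose AFRS worsens and who has sinus surgery during the treatment period.

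| Rule | Result |
|---|---|
| 1.3, footnote f | A page is completed in every case; AE or SAE left open |
| 8.1.2 | Surgery page; nothing said on an AE page |
| 10.3.1, procedures | The procedure is not the AE; the condition behind it is |
| 10.3.1, disease under study | No AE if the course is expected; an AE if more severe than expected |
| 10.3.1, exacerbation | AE |
| 10.3.1, lack of efficacy, first bullet | Not an AE or SAE in itself |
| 10.3.1, lack of efficacy, second bullet | An AE or SAE |
| 10.3.2 | If not an AE, not an SAE, unless local rules differ |

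No passage says which rule prevails.

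**Step 2. See how far the procedure bullet removes the conflict.** A page naming worsening AFRS satisfies both footnote f and the procedure bullet. But the condition behind surgery for AFRS is AFRS, so the disease-under-study bullet applies next. Footnote f is automatic at the point where that bullet asks for a judgment of severity against expectation. Expected worsening is not an empty category: Protocol 2.2 and 3.1 describe frequent relapse and repeat surgery. For those cases the exclusion bullet points to no AE, while footnote f requires a page. The exacerbation bullet and the second lack-of-efficacy bullet both favor recording.

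**Step 3. Trace an entry into the tables.** SAP 3.1 ends the treatment-emergent period 98 days after the last dose, and 98/7 = 14 weeks. Planned last doses are from Protocol 6.1.
- q2w: Week 50 + 14 = Week 64, the nominal end-of-study visit.
- q4w: Week 48 + 14 = Week 62.

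For a participant who completes treatment, an AE linked to surgery in follow-up is therefore almost always treatment-emergent. For one who stopped dosing early, the window closes 14 weeks after that person's own last dose, and a later event goes to the post-treatment tables.

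Surgery during the treatment period ends study treatment (Protocol 6.5.3 and 7.1.1), so a linked AE can also be counted as a TEAE leading to discontinuation.

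**Step 4. Size per participant.** The planned arm size is 31 (Protocol 4.1). If *k* participants enter a row only because of a surgery-linked entry, the arm's percentage rises by 100 × *k*/31:
- *k* = 1: 3.2 percentage points
- *k* = 2: 6.5 percentage points
- *k* = 3: 9.7 percentage points

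Two participants sharing a preferred term (6.5%) are enough to pass the 5% threshold of the common-TEAE table in SAP 3.6.2; one (3.2%) is not.

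**The case against.** The strongest reply has three parts.

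**The texts can mostly be read together.** Footnote f asks for a page when surgery occurs; it does not say the surgery is the event. Section 10.3.1 names the underlying condition as the AE, makes an exception for worsening beyond expectation, and lists exacerbation as an AE. This stands for many surgeries. It does not cover expected worsening, and it does not resolve the two lack-of-efficacy bullets.

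**The safety tables are descriptive and itemized.** No test is biased, an AFRS term would appear on its own preferred-term line, and SAP Appendix 3 summarizes rescue procedures separately. This also stands, and it limits the harm. It does not help with the any-TEAE, any-SAE and discontinuation totals, which cannot be separated by cause from the planned output.

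**Some readers will infer more than the documents support:**
- *Every sinus surgery becomes an SAE.* Footnote f covers only surgery performed in the treatment or follow-up period and leaves seriousness open.
- *Sites that follow Section 10.3 record nothing.* The severity exception, the exacerbation bullet and the second lack-of-efficacy bullet can each lead to an AE record.
- *A particular placebo excess arises from recording alone.* The documents give no surgery rate and no fraction that would be serious. The totals count participants with at least one event, so someone who already has another TEAE adds nothing to the any-TEAE row.

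**Conclusion.** The inconsistency is real and unranked, and it is clearest in the adjacent lack-of-efficacy bullets and in footnote f set against the exclusion of expected progression. The documents do not show that efficacy failures will be mixed into the safety tables. They show that this can happen, that it would depend on site interpretation, and that it would plausibly fall more on placebo.

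The total size is unknown. The 3.2 points per participant assume 31 treated per arm and a participant who would not otherwise be counted in that row. For the SAE row, the entry must also be serious. The primary efficacy analysis is unaffected. This should be corrected because the safety comparison is small and the remedy is cheap.

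**What to change.** **Protocol.** Reconcile footnote f, Section 8.1.2, the Section 10.3.1 bullets (including the two on lack of efficacy) and Section 10.3.2 into one rule. It should state whether surgery for AFRS leads to an AE or SAE page and, if so, under what term. Send the rule to all sites.

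**SAP 3.6.2.** Use the surgery eCRF page to flag AEs and SAEs linked to AFRS surgery, with the linking rule fixed before unblinding. That page identifies the participants. The documents do not say that it points to a specific AE record, so a short blinded check may be needed. Then show TEAEs, serious TEAEs and TEAEs leading to discontinuation with and without the flagged entries.

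**Cost.** A clarification memo and a few extra descriptive tables, based on a surgery page that is already collected.

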2 INTRODUCTION

Allergic fungal rhinosinusitis is a type 2 mediated disease characterized by thick mucus, opacification of the sinuses, and nasal polyps. Dupilumab is a fully human monoclonal antibody directed against the IL-4R α , which is a component of IL-4 receptors Type I and Type II, as well as the IL-13 type II receptor. The binding of dupilumab to IL-4R α results in blockade of IL-4 and IL-13 intracellular signaling.

As a targeted/specific immunomodulatory agent, dupilumab is expected to selectively inhibit type 2 inflammations and is designed to achieve the desired therapeutic effect without the side effects typically associated with the use of less selective immunosuppressants.

Both IL-4 and IL-13 signaling pathways are implicated in CRS and by blocking the activity of these cytokines, dupilumab has been shown to be an effective treatment for CRSwNP including improved sinus opacification, reduction in nasal polyp burden and improved symptom scores.

2.1 STUDY RATIONALE

Allergic fungal rhinosinusitis is a chronic disease of the sinuses characterized by a type 2 inflammatory response to the presence of fungal hyphae. There is a great unmet need to identify a therapy that can suppress disease progression and potentially limit the need for recurrent surgery or oral corticosteroid exposure. This indolent disease is chronic and is associated with a gradual progression, thick mucus and nasal polyps. Current treatment paradigms require endoscopic nasal sinus surgery including debridement of mucus and polypectomy, followed by a tapering schedule of adjuvant oral corticosteroids. The disease is chronic in nature, and can recur despite surgery, particularly with continued exposure to fungal spores in endemic areas. Patients with recurrence will need rescue therapy, including a short course of oral corticosteroids and even repeat surgery.

Allergic fungal rhinosinusitis is driven by a type 2 inflammatory response in the presence of fungal spores, and therefore is highly likely to respond to dupilumab treatment. The presence of type 2 inflammation is evidenced by polyp formation as well as responsiveness to corticosteroids. Molecular profiling has demonstrated elevations in type 2 inflammatory markers including IL-4, IL-5 (promoter of eosinophil survival, differentiation and taxis), and IL-13, eosinophil cationic protein (eosinophil activation product), eotaxins (eosinophil chemoattractants), P-glycoprotein (marker of eosinophilia, that correlates with Lund Mackay [LMK] score) and immunoglobulin E (IgE) from the nasal mucosa and local secretions (11, 12) as well as overexpression of eosinophilia-related genes (13). Whole gene microarray analysis from ethmoid mucosa has demonstrated an overexpression of type 2 inflammatory genes among patients with AFRS.

Dupilumab is a fully human monoclonal antibody directed against the IL-4R α , which is a component of IL-4 receptors type I and type II, as well as the IL-13 type II receptor. The binding of dupilumab to IL-4R α results in blockade of IL-4 and IL-13 intracellular signaling. As a targeted/specific immunomodulatory agent, dupilumab is expected to selectively inhibit type 2 inflammations and is designed to achieve the desired therapeutic effect without the side effects typically associated with the use of less selective immunosuppressants.

Both IL-4 and IL-13 signaling pathways are implicated in CRS, asthma and other atopic diseases and by blocking the activity of these cytokines, dupilumab has been shown to be an effective treatment for CRSwNP, a type 2 inflammatory process. This includes 2 successful Phase 3 studies of 24- and 52-weeks duration, in which 300 mg q2w of dupilumab used on top of topical corticosteroids (mometasone furoate nasal spray) in patients with CRSwNP demonstrated a positive benefit-risk and clinically significant efficacy across radiological, endoscopic, and clinical symptoms of disease, resulting in significant reduction in need for SCS and surgery (14). Therefore, given the high degree of overlap between the immunologic drivers for mucus production and nasal polyp formation, considering both AFRS and CRSwNP are a subtype of CRS and share common disease characteristics, including type 2 inflammatory pattern, as well as some elements of disease presentation, eg, sinus inflammation, nasal polyps, and symptoms like nasal congestion and rhinorrhea it is anticipated that dupilumab will have a similar impact on disease burden in patients with AFRS.

Dupilumab, therefore, offers promise of significant benefit above and beyond current standard of care in AFRS and may provide an alternative for those patients who relapse after surgery and may obviate the need for repeated SCS and/or surgeries.

A detailed description of the chemistry, pharmacology, efficacy, and safety of dupilumab is provided in the Investigator's Brochure (IB).

2.2 BACKGROUND

Disease Background and Unmet Medical Need

Allergic fungal rhinosinusitis is a disease driven by a type 2 inflammatory response to fungal spores that presents with a chronic and indolent course, mucous and nasal polyp formation in the sinuses and nasal cavity (2).

Allergic fungal rhinosinusitis is present worldwide, predominantly identified in regions with warm and humid climates such as the Southeastern United States (US) (15), and has also been described globally including Japan (16), Turkey (17), Saudi Arabia (18), and India (19). Although the disease is characterized by CRS, and all patients must have nasal polyps as part of the diagnostic criteria, AFRS represents a distinct disease that is driven by dynamic interplay between fungal spores and host defenses. The disease occurs in a younger population with a mean age in the 20s to 30s (2, 5). There may be a greater predominance of African Americans and some reports suggest a greater predominance among individuals with lower socioeconomic status (20). Patients with AFRS are more likely to have concomitant asthma than the general population, but the overall incidence is lower at approximately 25% (6). AFRS typically presents in young adults in their late teens and twenties, however there are rare case reports of AFRS in children between 6 to 12 years of age (9).

More often the presentation of AFRS is subtle and indolent. Patients typically complain of nasal airway obstruction developed gradually (1). Nasal discharge typically has a thick mucoid peanut-butter like appearance. Without timely intervention, possible complications in patients with AFRS can include visual disturbances, proptosis, facial deformity, and intracranial sequelae. The incidence of bony erosion in AFRS has been reported to be between 20% to 90% (21).

The CT findings can be distinctive and may include the presence of unilateral disease, hyperdensities, bony demineralization of the sinuses, and bone erosion of the sinuses. CT scans of the sinuses in AFRS patients typically show near-complete opacification with heterogeneous radiodensity (hyperdensities) of the soft tissue of the sinuses (21). Although there are rare cases of AFRS in children ≥ 6 to <12 years of age, in these children the disease commonly leads to facial dysmorphism in children. The growing facial skeleton of younger children may account for the higher degree of dysmorphism seen as compared to adults. Asymmetric disease and unilateral sinus disease are more frequent in children (above 6 years of age) compared with adults while incidence of bony erosion is comparable with adults (8, 9).

Allergic fungal rhinosinusitis is a disease marked by type 2 inflammation driven by dynamic interaction of fungal hyphae locked within thick sinus mucus and type 2 inflammatory responses. Patients have elevated serum IgE antifungal antibodies and eosinophils, and the inflammatory mucus is characterized by the presence of eosinophils (21). Patients with AFRS have notably higher levels of serum IgE antifungal antibodies than CRSwNP (3, 21). Molecular phenotyping has demonstrated that the epithelium of patients with AFRS shares many common overexpressed genes with CRSwNP (13). This includes type 2 inflammatory genes, including those involved with IgE and eosinophil chemotaxis and activation, such as eotaxin-3 (22). Large scale gene expression profiling including tissue from patients with CRSwNP and AFRS has demonstrated shared overexpression of type 2 inflammatory pathways including those involved with IL-4, IL-5, and IL-13 (13). However, molecular endotyping has also identified pathways that are distinct to AFRS, which differentiate AFRS from CRSwNP as a subtype of CRS demonstrating an extreme of type 2 inflammation such as the iCOS, CD28 and PKC Θ signaling pathways, which play pivotal roles in type 2 inflammatory effector function (7).

Allergic fungal rhinosinusitis is identified by distinct diagnostic criteria that were developed by Bent and Kuhn (4). This includes the presence of nasal polyps and characteristic CT opacification, as well as the presence of IgE mediated inflammatory response to fungal hyphae as characterized by specific IgE positivity or skin prick testing, as well as sheets of eosinophils presence in sinus mucus. Aspergillus species are the most commonly identified fungi. Other funguses include Bipolaris and Curvularia (3). In 1999, Ponikou showed that treating mucus with a reducing agent, dithiothreitol (DTT), could release fungi trapped within the mucin. Using this technique, his group showed positive fungal cultures from nasal secretions collected from 96% of chronic rhinosinusitis (CRS) patients and 100% of patients without CRS. Fungal staining has high variability (10-100% false positive rate) and low specificity. In practice this means that a negative fungal stain does not rule out the diagnosis of AFRS, while saprophytic fungal growth is not necessarily diagnostic of AFRS. This uncertainty is reflected in the fact that fungal culture is only considered supportive evidence in the Bent and Kuhn diagnostic criteria in contrast to the other four criteria which are key for the diagnosis (CT, polyps, elevated specific IgE, and eosinophilic mucin). Therefore, fungal culture is used as supportive evidence. However, the remainder of the Bent and Kuhn criteria is necessary for making the diagnosis of AFRS (23).

Except for the mildest cases, AFRS usually requires surgical intervention, followed by a prolonged course of adjuvant medical therapy (21). Medical therapy alone is regularly ineffective in alleviating symptoms and surgical intervention, alone or in combination with medical therapy is required (3). The large majority of patients will undergo surgical ESS with mucus debridement followed by adjuvant therapy including oral corticosteroid taper over 2 weeks

to 6 months with or without chronic topical (intranasal) corticosteroids (3, 21, 24). Recurrence can occur, and risk factors may include inadequate full debridement at the time of surgery or noncompliance with/inability to tolerate topical and oral corticosteroids (25). Overall recurrence rates after surgery are reported to range from 10% to 100% (3). The median interval for revision surgery in AFRS was much shorter than CRSwNP (2 versus 7 years) (26). Postoperative oral corticosteroids help decrease disease recurrence (21). However, even in AFRS patients treated with postoperative systemic steroids and with topical steroid, approximately 10% to 30% of patients experience disease recurrence within 6 months to 1 year after surgery (27, 28, 29). Despite the widespread acceptance of these treatment modalities, the optimal dose, duration, and tapering regimen of postoperative oral corticosteroids have not been addressed. A short-term oral corticosteroid rescue therapy can be considered for acute exacerbation. In the pediatric population, early efforts should be made to transition from a systemic regimen of corticosteroids to intranasal topical steroid therapy to avoid the side effects of systemic steroids (9). Multiple repeated oral corticosteroid rescue or long-term use of oral corticosteroids can cause significant side effects, including psychosis, insomnia, weight gain, poor control of glucose level, high blood pressure, Cushing's syndrome, adrenal insufficiency, osteoporosis, glaucoma, etc (24). Patients who continue to have progressive disease have increased risk for erosion of the bony sinuses, which can lead to facial deformities as well as increase the complexity and risk at the time of endoscopic surgery. The role of antifungals remains unclear and they are currently not recommended (10). There are currently no therapies that are approved specifically for the treatment of AFRS. There remains great unmet need in identifying novel therapies that address inflammatory underpinnings of the disease processes, minimizes the need for SCS and surgery and their associated side effects, prevents recurrence, prevents complications and bony erosion, and achieve a long-lasting disease control.

